5.4.1.2.2. Estimand of Time to Disease Recurrence

Objective: To evaluate disease recurrence in participants treated with guselkumab versus placebo after surgery

Estimand Scientific Question of Interest: What is the difference in time to disease recurrence at the main database lock, and thus considered to have benefited from guselkumab versus placebo?

Study intervention:

- Experimental: Guselkumab ^{CCI} at Week 0 and then ^{CCI} at Week 8, then ^{CCI} thereafter through the end of the total study period.
- Control: Matched placebo CCI at Weeks 0 and 8 and then CCI thereafter through the end of the total study period.

Population: Participants with recent (<49 days) qualifying surgery and no evidence of active Crohn's disease postoperatively.

Variable: The time to disease recurrence (as defined above) or experiencing ICE 1-3 presented below.

CONFIDENTIAL – FOIA Exemptions Apply in U.S.

Summary Measure (Population-level summary): Difference in the time to disease recurrence (as defined above) or experiencing ICE 1-3 presented below between guselkumab group and the placebo group.

Intercurrent events and their corresponding strategies:

The following are the ICEs considered for this study:

Table 10: Intercurrent Events and Corresponding Analysis Strategies for Disease Recurrence at Main Database Lock

Int loc	ercurrent Events (between baseline and main database k)	Analysis Strategy for Intercurrent Events
1.	A CD-related surgery (with the exception of minor procedures such as drainage of a superficial abscess or seton placement, etc.)	Composite Strategy: Participants are considered having disease recurrence if they experience any of these ICEs, prior to main database lock, as
2.	A prohibited change in CD medication (details in Appendix 9 Medications of Special Interest)	reflected in the variable definition.
3.	Discontinuation of study intervention due to lack of efficacy or an AE of worsening CD	
4.	Discontinuation of study intervention due to COVID-19 related reasons (excluding COVID-19 infection)	Treatment Policy: ICE4 and ICE5 will be ignored, and any data observed after the
5.	Discontinuation of study intervention due to reasons other than those in ICE 3 or 4	associated ICE event will be used for the analysis.

Abbreviation: AE=adverse event; CD=Crohn's disease; COVID-19= Coronavirus disease 2019; ICE=intercurrent event

Intercurrent events in categories 1 to 3 will be handled by the composite strategy. This estimand acknowledges that having an ICE in categories 1 to 3 is an unfavorable outcome. For participants experiencing ICEs in category 4 and 5, the treatment policy strategy will be used and considers the occurrence of ICE category 4 and 5 is irrelevant in defining the treatment effect and so observed values of the variable will be used, if available, regardless of the occurrence of ICE category 4 and 5.

5.4.1.2.3. Estimand of Abdominal Pain Free at Week 48

Objective: To evaluate abdominal pain scores in guselkumab versus placebo after surgery.

Estimand Scientific Question of Interest: What is the proportion of participants achieving abdominal pain free at Week 48, and thus considered to have benefited from guselkumab versus placebo?

Study intervention:

- Experimental: Guselkumab ^{CCI} at Week 0 and then ^{CCI} at Week 8, then ^{CCI} thereafter through the end of the total study period.
- Control: Matched placebo ^{CCI} at Weeks 0 and 8 and then ^{CCI} thereafter through the end of the total study period.

Population: Participants with recent (<49 days) qualifying surgery and no evidence of active Crohn's disease postoperatively.

Variable: A binary variable of abdominal pain free at Week 48 (abdominal pain [AP] score = 0) or experiencing ICEs 1-4 in Table 9.

Summary Measure (Population-level summary): Difference in proportions of the binary variable of abdominal pain free, as described above, between guselkumab group and the placebo group.

Intercurrent events and their corresponding strategies:

The same ICEs and corresponding strategies that are specified for primary endpoint of endoscopic recurrence prior to or at Week 48 will be used.

5.4.1.2.4. Estimand of Time-to-Recurrence of Symptoms

Objective: To evaluate symptoms such as stool frequency and abdominal pain scores in guselkumab versus placebo after surgery.

Estimand Scientific Question of Interest: What is the difference in time to symptoms at the main database lock, and thus considered to have benefited from guselkumab versus placebo?

Study intervention:

- Experimental: Guselkumab ^{CCI} at Week 0 and then^{CCI} at Week 8, then ^{CCI} thereafter through the end of the total study period.
- Control: Matched placebo CCI at Weeks 0 and 8 and then CCI thereafter through the end of the total study period.

Population: Participants with recent (<49 days) qualifying surgery and no evidence of active Crohn's disease postoperatively.

Variable: The time to symptoms (defined as time to attaining an AP mean daily score >1 (and also >1 point higher than baseline) along with stool frequency (SF) mean daily score >3 (and also >3 higher per day than baseline) for 2 consecutive weeks through Week 48) or experiencing ICE 1-3 in Table 10.

Summary Measure (Population-level summary): Difference in the time to symptoms (as defined above) or experiencing ICE 1-3 presented in Table 10 between guselkumab group and the placebo group.

Intercurrent events and their corresponding strategies:

The same ICEs and corresponding strategies that are specified for second secondary endpoint of time to disease recurrence will be used.

5.4.1.2.5. Estimand of Steroid Free Clinical Remission at Week 48

Objective: To evaluate the efficacy of guselkumab treatment at Week 48 compared with placebo in limiting steroid use and maintaining remission in the postoperative period.

Estimand Scientific Question of Interest: What is the proportion of participants achieving steroid free clinical remission at Week 48, and thus considered to have benefited from guselkumab versus placebo?

Study intervention:

- Experimental: Guselkumab CCI CCI at Week 0 and then CCI at Week 8, then CCI thereafter through the end of the total study period.
- Control: Matched placebo CCI at Weeks 0 and 8 and then CCI thereafter through the end of the total study period.

Population: Participants with recent (<49 days) qualifying surgery and no evidence of active Crohn's disease postoperatively.

Variable: A binary variable of steroid free clinical remission at Week 48 (defined as CDAI <150 and no corticosteroids within 30 days) or experiencing ICEs 1-4 in Table 9.

Summary Measure (Population-level summary): Difference in proportions of the binary variable of steroid free clinical remission, as described above, between guselkumab group and the placebo group.

Intercurrent events and their corresponding strategies:

The same ICEs and corresponding strategies that are specified for primary endpoint of endoscopic recurrence prior to or at Week 48 will be used.

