- OR developing a new intra-abdominal abscess more than three months after the date of the index surgery.

Participants who have confirmed endoscopic recurrence at Week 24 or Week 48 and cross over to open-label guselkumab treatment will be censored at cross over for the time to disease recurrence endpoint.

Time-to-disease recurrence at the main study database lock, which will incorporate all available follow-up of enrolled participants at the time that the last participant dosed has completed the Week 48 study procedures, including the ileocolonoscopy.

- Abdominal pain free at Week 48: abdominal pain [AP] score = 0.
- **Time-to-recurrence of symptoms**: defined as time to attaining an AP mean daily score >1 (and also >1 point higher than baseline) along with stool frequency (SF) mean daily score >3 (and also >3 higher per day than baseline) for 2 consecutive weeks through Week 48.
- Steroid free clinical remission at Week 48: defined as CDAI <150 and no corticosteroids within 30 days.

Specific primary, secondary, and exploratory endpoints, along with definitions, are provided in Section 5, Statistical Analyses, and the study protocol.

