5.4.1.1. Definition of Endpoint(s)

Clinical remission without disease recurrence is a composite endpoint defined by the following:

- CDAI < 150 at Week 48 and
- No endoscopic recurrence as defined by Rutgeerts score < i2a by Week 48 and
- Have not experienced a disease recurrence as defined below

Disease recurrence is a composite endpoint defined by the following:

- A ≥ 70-point increase from baseline in CDAI score at beyond 8 weeks after randomization; and a CDAI score of ≥ 200 **and** evidence of endoscopic recurrence. Endoscopic recurrence is defined as a modified Rutgeerts score of ≥ i2a at the anastomotic site or its equivalent elsewhere in the GI tract, unless a stool test for C. difficile toxin or other enteric pathogen is positive
- In event of a positive test for enteric pathogen including C. difficile toxin, the underlying infection should be treated and if ileocolonoscopy has not yet been performed, it should only be done when the infection has resolved, and if disease recurrence threshold is still met
- OR initiation of a physician-prescribed corticosteroids, or an increase in the dose of steroids already being taken (by greater than 5 mg/day), for over one week for the treatment of CD and evidence of endoscopic recurrence as described above, unless a stool test for C. difficile toxin or other enteric pathogen is positive
- OR a new draining external fistula
- OR the reopening and draining of a previously existing external fistula
- OR developing a new internal fistula
- OR developing a new perianal abscess
- OR developing a new intra-abdominal abscess more than three months after the date of the index surgery

Participants who have confirmed endoscopic recurrence without disease recurrence at Week 24 or Week 48 and cross over to open-label guselkumab treatment will be censored at cross over for the time to disease recurrence endpoint.

Abdominal pain free at Week 48 is defined as abdominal pain (AP) score = 0 at Week 48

Time-to-recurrence of symptoms is defined as time to attaining an AP mean daily score >1 (and also >1 point higher than baseline) along with stool frequency (SF) mean daily score >3 (and also >3 higher per day than baseline) for 2 consecutive weeks through Week 48. Participants who cross over to open-label guselkumab treatment and do not have recurrence of symptoms will be censored at cross over for the time to recurrence of symptoms endpoint.

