Summaries of median survival time and interquartile range of survival time by treatment group will be provided. The log-rank test will be used to compare disease recurrence distribution between the two treatment groups. The Kaplan-Meier method will be used to estimate the distribution of disease recurrence for each treatment. The treatment effect (hazard ratio) and its two-sided 95% confidence intervals are to be estimated using Cox regression model with treatment and stratification factors. Participants who have not achieved disease recurrence during the main study period at the database lock will be censored at the last visit. Participants without any post-baseline follow-up will be censored at randomization.

Estimators of Steroid Free Clinical Remission at Week 48

Summaries of the proportion of participants that achieve steroid free clinical remission by treatment group will be provided. To compare the guselkumab versus placebo group for the first secondary endpoint, the CMH chi-square test (2-sided) will be used with stratification of clinical remission status at baseline (CDAI < 150, CDAI \ge 150), region (North America, Western Europe, rest of world) and number of prior surgeries (1 surgery versus > 1 surgery, with the qualifying surgery counting as 1 surgery).

After accounting for the ICE strategies, missing data will be imputed by multiple imputation. Multiple imputation will be used for imputing missing data under the assumption that the data are MAR. The analysis will impute the missing Rutgeerts score at Week 48 using the analysis method and ancillary variables as described in Table 13. The responses at Weeks 48 will be derived from the imputed datasets and combined for analysis.

Variable	MI specification	Analysis method/Summary statistics
CDAI score at Week 48	Multiple imputation with monotone regression of total scores	 MIdataset1 (N=200, Seed=5748941) Imputation variables: CDAI at Week 48 Ancillary variables: Treatment group, baseline Rutgeerts score, history of primary non-response to at least one approved ADT (Yes, No), clinical remission status at baseline (CDAI < 150, CDAI ≥ 150), region (North America, Western Europe, rest of world) and number of prior surgeries (1 surgery versus > 1 surgery, with the qualifying surgery counting as 1 surgery)

 Table 13:
 Multiple Imputation Methods for CDAI at Weeks 48

Type I error will be controlled over the primary and secondary endpoints hierarchically. The sequence of tests will be:

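### Time to recurrence of symptoms counts symptoms only to Week 48, while its ICE events and censoring run to the main database lock and its estimator text names disease recurrence

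*SAP*

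**What the plan says.** **Endpoint.** SAP 1.1 and 5.4.1.1, and Protocol Section 3, define the event by abdominal pain and stool frequency thresholds, ending "also >3 higher per day than baseline) for 2 consecutive weeks through Week 48".

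**Estimand (SAP 5.4.1.2.4).** The scientific question is "What is the difference in time to symptoms at the main database lock". The variable reads "for 2 consecutive weeks through Week 48) or experiencing ICE 1-3 in Table 10". The bracket closes after Week 48, so that limit covers the symptom criteria but not the ICEs. The section then adds: "The same ICEs and corresponding strategies that are specified for second secondary endpoint of time to disease recurrence will be used".

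**Imported table (SAP 5.4.1.2.2).** Table 10 is titled "Intercurrent Events and Corresponding Analysis Strategies for Disease Recurrence at Main Database Lock". Its composite rule is "Participants are considered having disease recurrence if they experience any of these ICEs, prior to main database lock, as" reflected in the variable definition.

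**Cross-over (SAP 5.4.1.1).** "Participants who cross over to open-label guselkumab treatment and do not have recurrence of symptoms will be censored at cross over". No Week 48 censoring rule accompanies this.

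**Estimator (SAP 5.4.1.3, Estimators of Recurrence of Symptoms).** The log-rank comparison and the Kaplan-Meier estimate are both described as being of disease recurrence. The censoring rule is "Participants who have not achieved disease recurrence during the main study period at the database lock will be censored at the last visit". The same sentences appear under Estimators of Disease Recurrence.

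Protocol 9.4.3 says only that this endpoint is analysed similarly to time to disease recurrence, and sets no horizon of its own.

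**The concern.** A time-to-event endpoint needs one period over which all its event types can occur, and a censoring rule that ends follow-up when that period ends. Here the symptom component closes at Week 48 while the ICE component stays open to the main database lock. By the plan's own estimate that lock comes 12 to 30 months after entry (SAP 1.2.1).

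A participant with a CD-related surgery, a prohibited medication change or a discontinuation for lack of efficacy at, say, month 20 would count as a symptom-recurrence event. A participant whose symptoms returned in the same month would not. Late events in test 5 would then be ICEs alone, and the hazard ratio would mix a symptom-or-ICE composite before Week 48 with an ICE-only comparison after it. The carried-over estimator text leaves no correct statement of what is tested or when an event-free participant is censored.

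**Working it through.** **Step 1. Horizon of each element.**

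| Element | Source | Horizon or event |
|---|---|---|
| Endpoint definition | SAP 1.1, 5.4.1.1; Protocol 3 | Week 48 |
| Scientific question | SAP 5.4.1.2.4 | Main database lock |
| Symptom events in the variable | SAP 5.4.1.2.4 | Week 48 |
| ICE 1-3 events in the variable | SAP Table 10, by reference | Main database lock |
| Cross-over | SAP 5.4.1.1 | Censored at cross-over |
| Other event-free participants | SAP 5.4.1.3 | Last visit in the main study period |
| Event tested and plotted | SAP 5.4.1.3 | Disease recurrence |

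No rule closes the gap between the Week 48 rows and the database-lock rows. SAP Appendix 9 narrows it slightly: within ICE 2, the items on immunomodulators and on steroids for reasons other than worsening CD are limited to Week 48. Surgery (ICE 1), discontinuation (ICE 3), other prohibited medications and steroid changes for worsening CD have no such limit.

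**Step 2. Reproduce the plan's follow-up.** Inputs from SAP Section 3: 18 months' accrual, 30 months in total, 25% / 35% / 40% enrolled per 6-month block, 15% annual dropout. With uniform entry within blocks, the mean entry times are 3, 9 and 15 months.

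Mean follow-up without dropout = 30 - (0.25×3 + 0.35×9 + 0.40×15) = 30 - 9.9 = 20.1 months. The plan states approximately 20.

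With exponential dropout at 15% per year, simulation gives a median of 17.5 months. The plan states approximately 18. Both figures reproduce.

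**Step 3. Follow-up after Week 48.** Week 48 = 48×7/30.4375 = 11.04 months. Minimum planned follow-up is 12 months, so without dropout everyone passes it.

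- No dropout: 20.1 - 11.04 = 9.06 months; 9.06/20.1 = 45%.
- With dropout (simulated): 7.21 of 17.46 months = 41%. About 86% of participants reach Week 48.

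These are upper bounds, because earlier events and censoring at cross-over remove time.

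**Step 4. Allow for cross-over at Week 48.** Centrally confirmed endoscopic recurrence at Week 48 leads to cross-over (Protocol 6.5.1; SAP 1.2.1), and this endpoint censors there. The planning rates for endoscopic recurrence are 50% and 30%, or 40% overall with equal arms. Assume, as a simplification, that all 40% cross over at Week 48.

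- No dropout: (0.6×9.06)/(20.1 - 0.4×9.06) = 5.44/16.48 = 33%.
- With dropout: (0.6×7.21)/(17.46 - 0.4×7.21) = 4.33/14.58 = 30%.
- By arm, no dropout: placebo (0.5×9.06)/(20.1 - 0.5×9.06) = 4.53/15.57 = 29%; guselkumab (0.7×9.06)/(20.1 - 0.3×9.06) = 6.34/17.38 = 36%.

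**Step 5. What cannot be computed.** The documents give no event rate for this endpoint and no rate of ICEs 1-3 after Week 48. Neither the number of late ICE events nor the change in the test can be derived.

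**The case against.** **Week 48 is evidently intended.** Every endpoint definition says so, and a careful programmer would probably apply it. That stands as a reading of intent. However, the question, the ICE window and the censoring rule all say otherwise, and a confirmatory test should not rest on a guess.

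**Person-time is the wrong measure.** Log-rank and Cox analyses use risk sets at event times, so event-free time after Week 48 adds nothing by itself. This stands. A reader might infer that 45% of the analysis is distorted; the documents do not support that. Only late ICE events matter, and their number is unknown.

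**Test 5 repeats test 3.** A reader might infer this from the estimator paragraph. The heading, the estimand, the separate definition with its own cross-over rule, and the listing in the test sequence all identify a distinct endpoint. The paragraph is copied text. The same section makes similar slips, calling abdominal pain and steroid-free remission the first secondary endpoint.

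**Type I error.** A reader might also infer inflation from the endpoint's place in the sequence. The same composite rule applies to both arms, and no inflation is shown. The problem is what the estimand means.

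**No practical effect here.** The SAP Introduction reports that the study was discontinued with four subjects enrolled and that the planned analyses no longer apply. This stands for this trial's results.

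**Conclusion.** The point holds as an inconsistency in the written rules for a fifth-ranked, alpha-controlled endpoint. Followed as written, ICEs 1-3 after Week 48 would count as recurrence of symptoms when symptoms themselves no longer could. The estimator also names the wrong event.

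Exposure to the mismatch is at most about 45% of planned follow-up, or 41% with dropout. It is about 33% (30% with dropout) if 40% of participants cross over at Week 48. These figures rest on the plan's accrual and dropout assumptions, uniform entry within blocks and, for the lower pair, cross-over of everyone with assumed endoscopic recurrence exactly at Week 48. They do not show the size or direction of any effect on the test.

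The primary analysis and tests 2-4 are unaffected. As the analyses are kept only for reference, the value of correcting the text lies in any later use of this SAP as a template.

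**What to change.** Adopt Week 48, the horizon in the SAP's own endpoint definition, throughout:

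- In SAP 5.4.1.2.4, change the scientific question to refer to Week 48.
- State there that ICEs 1-3 count as events for this endpoint only through Week 48, and that such an event is recurrence of symptoms. Do this in the section itself or in a separate ICE table, not by bare reference to Table 10.
- In SAP 5.4.1.3, under Estimators of Recurrence of Symptoms, replace disease recurrence with recurrence of symptoms in the log-rank, Kaplan-Meier and censoring sentences.
- Censor event-free participants at the earliest of cross-over, last visit and Week 48. Keep the existing rule for participants with no post-baseline follow-up.

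The cost is SAP wording only, with no new data, visits or change in conduct.

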5.4.1.3. Analysis Methods

The analyses of the secondary endpoints will be based on the Full Analysis Set (FAS), which includes all randomized participants. Participants will be analyzed according to the intervention group to which they were randomized regardless of the study intervention they actually received.

Estimators of Clinical Remission at Week 48 without Disease Recurrence

Summaries of the proportion of participants that achieve clinical remission without disease recurrence by treatment group will be provided. To compare the guselkumab versus placebo group for the first secondary endpoint, the CMH chi-square test (2-sided) will be used with stratification of clinical remission status at baseline (CDAI < 150, CDAI \ge 150), region (North America, Western Europe, rest of world) and number of prior surgeries (1 surgery versus > 1 surgery, with the qualifying surgery counting as 1 surgery).

After accounting for the ICE strategies, missing data will be imputed by multiple imputation. Multiple imputation will be used for imputing missing data under the assumption that the data are MAR. The analysis will impute the missing Rutgeerts score at Week 48 using the analysis method and ancillary variables as described in Table 11. The responses at Weeks 48 will be derived from the imputed datasets and combined for analysis.

Variable	MI specification	Analysis method/Summary statistics
CDAI score at Week 48	Multiple imputation with monotone regression of total scores	 MIdataset1 (N=200, Seed=5748941) Imputation variables: CDAI at Week 48 Ancillary variables: Treatment group, baseline Rutgeerts score, history of primary non-response to at least one approved ADT (Yes, No), clinical remission status at baseline (CDAI < 150, CDAI ≥ 150), region (North America, Western Europe, rest of world) and number of prior surgeries (1 surgery versus > 1 surgery, with the qualifying surgery counting as 1 surgery)

Table 11:Multiple Imputation Methods for CDAI at Weeks 48

Estimators of Disease Recurrence

Summaries of median survival time and interquartile range of survival time by treatment group will be provided. The log-rank test will be used to compare disease recurrence distribution between the two treatment groups. The Kaplan-Meier method will be used to estimate the distribution of disease recurrence for each treatment. The treatment effect (hazard ratio) and its two-sided 95% confidence intervals are to be estimated using Cox regression model with treatment and stratification factors. Participants who have not achieved disease recurrence during the main study period at the database lock will be censored at the last visit. Participants without any post-baseline follow-up will be censored at randomization.

Estimators of Abdominal Pain Free at Week 48

Summaries of the proportion of participants that achieve abdominal pain free by treatment group will be provided. To compare the guselkumab versus placebo group for the first secondary endpoint, the CMH chi-square test (2-sided) will be used with stratification of clinical remission status at baseline (CDAI < 150, CDAI \ge 150), region (North America, Western Europe, rest of world) and number of prior surgeries (1 surgery versus > 1 surgery, with the qualifying surgery counting as 1 surgery).

After accounting for the ICE strategies, missing data will be imputed by multiple imputation. Multiple imputation will be used for imputing missing data under the assumption that the data are MAR. The analysis will impute the missing Rutgeerts score at Week 48 using the analysis method and ancillary variables as described in Table 12. The responses at Weeks 48 will be derived from the imputed datasets and combined for analysis.

Variable	MI specification	Analysis method/Summary statistics
AP score at Week 48	Multiple imputation with monotone regression of total scores	 MIdataset1 (N=200, Seed=5748941) Imputation variables: AP score at Week 48 Ancillary variables: Treatment group, baseline Rutgeerts score, history of primary non-response to at least one approved ADT (Yes, No), clinical remission status at baseline (CDAI < 150, CDAI ≥ 150), region (North America, Western Europe, rest of world) and number of prior surgeries (1 surgery versus > 1 surgery, with the qualifying surgery counting as 1 surgery)

Table 12:	Multiple Imputation Methods for AP Score at Weeks 48
-----------	--

Estimators of Recurrence of Symptoms

Summaries of median survival time and interquartile range of survival time by treatment group will be provided. The log-rank test will be used to compare disease recurrence distribution between the two treatment groups. The Kaplan-Meier method will be used to estimate the distribution of disease recurrence for each treatment. The treatment effect (hazard ratio) and its two-sided 95% confidence intervals are to be estimated using Cox regression model with treatment and stratification factors. Participants who have not achieved disease recurrence during the main study period at the database lock will be censored at the last visit. Participants without any post-baseline follow-up will be censored at randomization.

Estimators of Steroid Free Clinical Remission at Week 48

Summaries of the proportion of participants that achieve steroid free clinical remission by treatment group will be provided. To compare the guselkumab versus placebo group for the first secondary endpoint, the CMH chi-square test (2-sided) will be used with stratification of clinical remission status at baseline (CDAI < 150, CDAI \ge 150), region (North America, Western Europe, rest of world) and number of prior surgeries (1 surgery versus > 1 surgery, with the qualifying surgery counting as 1 surgery).

After accounting for the ICE strategies, missing data will be imputed by multiple imputation. Multiple imputation will be used for imputing missing data under the assumption that the data are MAR. The analysis will impute the missing Rutgeerts score at Week 48 using the analysis method and ancillary variables as described in Table 13. The responses at Weeks 48 will be derived from the imputed datasets and combined for analysis.

Variable	MI specification	Analysis method/Summary statistics
CDAI score at Week 48	Multiple imputation with monotone regression of total scores	 MIdataset1 (N=200, Seed=5748941) Imputation variables: CDAI at Week 48 Ancillary variables: Treatment group, baseline Rutgeerts score, history of primary non-response to at least one approved ADT (Yes, No), clinical remission status at baseline (CDAI < 150, CDAI ≥ 150), region (North America, Western Europe, rest of world) and number of prior surgeries (1 surgery versus > 1 surgery, with the qualifying surgery counting as 1 surgery)

 Table 13:
 Multiple Imputation Methods for CDAI at Weeks 48

Type I error will be controlled over the primary and secondary endpoints hierarchically. The sequence of tests will be:

- 1. Endoscopic recurrence prior to or at Week 48
- 2. Clinical remission without disease recurrence at Week 48
- 3. Time-to-disease recurrence
- 4. Abdominal pain free at Week 48
- 5. Time-to-recurrence of symptoms
- 6. Steroid free clinical remission at Week 48

